#### Risks of fasting

##### 8 hours before the fasting visits indicated in Study Flowchart section 2.2.1

Fasting for blood work is common and carries little risk. Participants may feel tired, hungry or irritable until they are served the standardized breakfast upon arrival.

Participants who are diabetic have relatively greater risks of hypoglycemia, but the PI/study clinician will guide these individuals, and possibly adjust their medications as needed to minimize these risks.

### Overall subject burden

- Subject burden is a possibility due to the number of visits and particularly during the comprehensive physical assessment battery that is completed as part of the protocol. However, as noted in the Methods, precautions have been integrated with the assessments to minimize risk to the participants. Rest periods are provided after each active functional assessment, moreover, active functional assessments alternate with ones that are completed at rest (questionnaires). Furthermore, at the end of each assessment and before the next functional assessment, and the rate of perceived exertion (RPE) is reassessed to evaluate fatigability and to make sure that the subject has returned to baseline of physiological and subjective parameters prior to the next test. The consent language includes that participants may withdraw at any time. The consent form includes language and PI and the study coordinator will be sure that participants understand the number, duration and activity for each visit, so as to fully inform potential participants on this issue.

### **6.2 ALTERNATIVE TREATMENTS**

The alternative treatments for the participants participating in this investigation are to continue their medical care under the direction of their primary physicians.

### **6.3 POTENTIAL BENEFITS**

There may be no direct medical benefit to participants in the study. It is hoped that researchers will learn more about the effectiveness of nitrite capsule supplements to improve strength, gait speed and balance. Oral nitrite may also increase efficiency of work by reducing their oxygen uptake required for the same work intensity. We hope the information learned from this study will benefit other older patients in the future.

## **7. RISKS MANAGEMENT PROCEDURES**

### **7.1 PROTECTION AGAINST RISKS**

#### General Risks of Study Protocol and Procedures

All research interventions/activities will be conducted in private patient care areas. The collection of sensitive information about participants is limited to the amount necessary to achieve the aims of the research, so that no unneeded sensitive information is being collected.

All demographic and clinical information about the subject will be stored in an electronic password-guarded study database under the supervision of the Investigator for this protocol.

The Center for Research on Health Care Data Center (CRHC-DC) at the University of Pittsburgh

Data will be maintained by the CRHC Data Center with MS SQL Server. SQL Server is designed for large relational databases and is a stable platform in which to house large volumes of data. All tables within SQL will be linked with a key identifier. SQL enables the system programmers to quickly generate custom datasets based on specific analyses. Additionally, SQL has a reporting mechanism that enables one of our system programmers to quickly generate reports as needed for the study. Data entered by clinical site personnel will be automatically added to the relational database stored on Data Center servers.

The EWI (Enterprise Web Infrastructure) is backed up with the Symantec NetBackup system. The backup images are processed through an IBM ProtectTier appliance and stored on IBM DS8870 storage arrays. All EWI servers get a daily operating system backup in the form of a full or differential backup. The backup schedule has daily differential and bi-weekly full backups for all EWI servers. The backup images have a retention period of 60 days. They are replicated to a secondary IBM DS8870 storage array located at Posvar Hall. This protects the backups images in the event of a catastrophic event at the RIDC data center.

EWI sites with a backend database server also receive a daily backup. All EWI database servers have a daily full backup and daily log backups. EWI database servers running MS SQL Server utilize a specialized NetBackup SQL backup agent. Any EWI database server running MySQL have a daily backup in the form of daily local dump and then have the exported database files backed up during the daily operating system backup. These again are replicated to the Posvar site. The backup methods used are proven methods for recovery. Partial file restores and full site restores have been performed upon a request from a department.

The Data Center is complaint with the FDA 21 CFR part 11 protocols. Access to data will be controlled through password and authentication policies. Only approved individuals will have access to data. Password policies control the length and variability of the user password selection. Audit trails will be implemented to log date, time, individual, changed values, and rationale for all data changes.

We have three high-end machines dedicated to statistical analyses. These machines contain up to 8 Xeon processors and up to 32gb or RAM with stripped raided SCSI high end performance hard drives. This provides a framework to manipulate and analyze very large datasets in an efficient and time effective manner.

The CRHC-DC biostatistical group uses current versions of SAS, R, and Stata for all data manipulation, statistical analyses, and reporting with set guidelines for code documentation and reproducibility. In addition, the statisticians use M-Plus and StatXact for specific types of analyses or simulations.

Specimens will be stripped of subject identifiers and stored according to a similar coding protocol as described above. These specimens will be stored safely in the custody of the Investigator responsible for the individual assays. The Investigators will limit future access to any remaining sample to only those investigators with prior IRB approval for their studies.

All staff involved in this study are properly credentialed and instructed in the areas of testing, confidentiality, and safety.

The Investigator will retain the data for the entire period of this study and will retain the specified records and reports for up to two years after the marketing application is approved for the investigational drug; or, if a marketing application is not submitted or approved for the investigational drug, until two years after investigations under the IND have been discontinued and the FDA so notified. The Investigator may continue to use and disclose participants' de-identified information for the purpose of this study for a minimum of seven years after final reporting or publication of the study. If the subject and/or legal representative decide to withdraw or be withdrawn from study participation, they may request that the study data and samples be destroyed. Subject names or other directly identifiable information will not appear on any reports, publications, or other disclosures of clinical study outcomes.

If applicable, any clinical study data that will be recorded directly on the CRF or electronic database whereupon the CRF/electronic data is to be considered the Source Data. Source Data are the clinical findings and observations, laboratory and test data, and other information contained

in Source Documents. Source Documents are the original records (and certified copies of original records; including, but not limited to, hospital medical records, physician or office charts, physician or nursing notes, subject diaries or evaluation checklists, pharmacy dispensing records, recorded data from automated instruments, x-rays, etc. When applicable, information recorded on the CRF shall match the Source Data recorded on the Source Documents. Describe the procedures for accounting for any missed, unused, and/or spurious data.

## 7.2 PROTECTION AGAINST POTENTIAL RISKS OF EXPERIMENTAL INTERVENTION

- Involvement by trained staff/investigators with experience in the administration of the study drug: [name], PI, and physician Co-I, [name] are principally responsible for monitoring and protecting the safety of participants' use of sodium NO2. Their combined experience in the use of the study drug is adequate to protect against (the relatively low) risks.
- Continuous monitoring by the Data and Safety Monitoring Board.
- Required Education in the Protection of Human Research Participants: The Principal Investigator and all sub-investigators listed on the University of Pittsburgh HRPO approved protocol are required to complete the Collaborative Institutional Training Initiative (CITI) courses in research fundamentals, including Human Participants Research and Responsible Conduct of Research. Staff will complete these courses as well, prior to any subject contact. Investigators and staff with subject contact will also complete the Good Clinical Practice module. Investigators with an identified Conflict of Interest (COI) will complete the COI module. These web-based tutorials are a requirement of the HRPO for investigators prior to protocol submission

## 8. ADVERSE EVENTS

The proposed study will use the FDA definition of adverse events (AE) and serious adverse events (SAE). Any SAE, which is unexpected and related to study intervention, will be reported immediately to the IRB and FDA and will include all known details regarding the nature of the SAE. In the event that a participant either withdraws from the study or the investigators decide to discontinue a participant due to a SAE, the participant will be monitored by the PI and treating investigator until (a) a resolution is reached (e.g., the problem has resolved or stabilized with no further change expected), (b) the SAE is determined to be clearly unrelated to the study intervention, or (c) the SAE results in death. Outcomes of SAEs not previously reported will be reported to the sponsor, IRB and FDA via a follow-up report. A summary of the SAEs that occurred during the previous year will be included in the FDA annual progress report as well as in the annual IRB renewal.

The severity of adverse changes in physical signs or symptoms will be classified as follows:

- Grade 1 (Mild): asymptomatic or mild symptoms; clinical or diagnostic observation only; intervention not indicated.
- Grade 2 (Moderate): minimal, local or noninvasive intervention indicated; limiting age-appropriate ADL (Activities of Daily Living).
- Grade 3 (Severe): medically significant but not immediately life-threatening; hospitalization or prolongation of hospitalization indicated; disabling; limiting self-care/ADL.
- Grade 4 (Life-threatening): consequences; urgent intervention indicated.

- Grade 5 (Death): event is a direct cause of death.

## 8.1 REPORTABLE ADVERSE EVENTS

For this study, a serious adverse event is any untoward clinical event that is thought by either the Principal Investigator, [name] or the sponsor, [name] to be unexpected and at least possibly related to the study and results in any of the following:

1. Death
2. A life-threatening adverse event
3. Inpatient hospitalization or prolongation of an existing hospitalization
4. A persistent or significant incapacity or substantial disruption of the ability to conduct normal life functions
5. A congenital anomaly or birth defect
6. Important medical events that may not result in death, be life threatening, or require hospitalization.
7. Hospitalization may be considered serious when, based upon appropriate medical judgment, they may jeopardize the patient, or subject, and may require medical, or surgical intervention to prevent one of the serious outcomes listed above.

If clinically important and unexpected adverse experiences or clinically important study-related adverse experiences occur, they will be recorded on the adverse event case report form.

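### Section 8.1 makes unexpectedness and possible relatedness part of what an SAE is, while Section 8 uses them to select SAEs for immediate reporting

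*Combined protocol and SAP*

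**What the plan says.** Section 8 (Adverse Events) begins: "The proposed study will use the FDA definition of adverse events (AE) and serious adverse events (SAE". It then gives the immediate reporting rule: "Any SAE, which is unexpected and related to study intervention, will be reported immediately to the IRB and FDA". For a participant who leaves the study because of an SAE, "the participant will be monitored by the PI and treating investigator until" one of three endpoints is reached; the second, clause (b), is that "the SAE is determined to be clearly unrelated to the study intervention". Two further duties in Section 8 attach to the SAE label with no condition on expectedness: "Outcomes of SAEs not previously reported will be reported to the sponsor, IRB and FDA via a follow-up report", and "A summary of the SAEs that occurred during the previous year will be included in the FDA annual progress report", with the same summary going into the annual IRB renewal.

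Section 8.1 (Reportable Adverse Events) is built differently. It states what a serious adverse event is for this study: an untoward clinical event that the PI or the sponsor thinks "to be unexpected and at least possibly related to the study and results in any of the following". The outcome list follows, including "Inpatient hospitalization or prolongation of an existing hospitalization".

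Section 8.2 and Section 10 name seriousness, unexpectedness and association with study drug or procedures as three separate conditions for expedited reports. Section 8.2 also sends every AE and SAE to the DSMB each quarter. Section 9.2 has staff report all AEs and SAEs to an Investigator, who reports them to the IRB under institutional requirements; they should also reach the IND sponsor.

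**The concern.** Whether an event is serious, whether it was expected and whether it is related are normally three separate judgements. Section 8.1 folds the second and third into the first. A serious event then keeps the SAE label only if at least one of two people, the PI or the sponsor, thinks it both unexpected and at least possibly related.

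At stake is which events are counted as SAEs and which follow-up obligations apply. Two staff members following different sections could produce different annual SAE counts from the same records. The protocol also does not say what reference decides whether an event was expected, so the 8.1 filter has no fixed edge.

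**Working it through.** The plan gives no figure on this point and no arithmetic applies. The check is to pass the same events through both sections, and then through each duty that uses the label.

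**Step 1: classify.** Take an inpatient hospitalization, an outcome listed in 8.1. The text of the FDA definition is not in the documents, so I assume that it also counts a hospitalization as serious.

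| Judgement by PI and sponsor | Section 8, natural reading | Section 8.1, literal |
|---|---|---|
| A. Unexpected, related | SAE, reported immediately | SAE |
| B. Expected, related | SAE, not immediate | not an SAE |
| C. Unexpected, unrelated from the outset | SAE, not immediate | not an SAE |
| D. Expected, unrelated | SAE, not immediate | not an SAE |
| E. Unexpected, first thought possibly related, later found unrelated | SAE; monitoring can end under clause (b) | SAE when first judged |

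The sections agree on A and, at first judgement, on E. They differ on B, C and D.

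**Step 2: follow B, C and D through the duties.**

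- *FDA annual summary (Section 8).* Keyed to the SAE label with no filter of its own. B, C and D drop out under 8.1.
- *Outcome follow-up report to sponsor, IRB and FDA (Section 8).* Also keyed to the label. B, C and D drop out. The sponsor and IRB still have the Section 9.2 route for the event; that section gives no such route to FDA.
- *IRB renewal summary (Section 8).* The events leave the SAE summary, but Section 9.2 provides for reporting them to the IRB as AEs.
- *Monitoring after leaving because of an SAE (Section 8).* Clause (b) ends it once the event is clearly unrelated, so the loss is mainly for B.
- *Quarterly DSMB report (8.2) and reports to Investigator, IRB and IND sponsor (9.2).* These cover all AEs. B, C and D remain and lose only the label.
- *Expedited reports (8, 8.2, 10).* The immediate, 24-hour, 48-hour and 15-day rules carry their own conditions on expectedness and relatedness or association. The 7-day FDA notice depends on the event being fatal or life-threatening, not on the SAE label. No change is shown.

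**Step 3: the reference for expectedness.** Section 6.1.1 lists symptoms the investigators anticipate, with hypotension shown as frequent in older participants at higher nitrite doses and seizure and coma as rare. Section 6.1.2 lists procedure risks. Neither is identified as the reference for expectedness, and neither is ruled out. If Section 6 were the reference, a hospitalization for drug-related hypotension could fall in row B.

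**The case against.** Four points can be made on the other side.

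- *Clause (b) does not prove that unrelated events are SAEs from the start.* It also fits 8.1, as row E shows. This stands, and the finding does not rest on that clause.
- *The commas in the Section 8 reporting rule allow the condition to be read as describing every SAE.* That is possible, but less natural. It would also make the separate conditions in 8.2 and 10 redundant. Redundancy is not a contradiction, but it favours the selective reading.
- *The 8.1 heading shows that a reporting filter was intended.* Probably so. The sentence nevertheless defines a serious adverse event, and does so specifically for this study, so staff could reasonably let it override the general statement in Section 8.
- *The events still reach the oversight bodies.* This largely stands for the DSMB, IRB and IND sponsor, and limits the consequence.

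A reader might go further and infer that serious drug harms would be hidden from the DSMB, or that expedited reports would be missed. Sections 8.2 and 9.2 do not support that. Nor do the documents show that the comparison by arm in Section 2.4.3 is distorted: it names hospitalizations, urgent or ER visits and deaths rather than SAEs, and the weekly calls ask about ER visits and hospitalizations.

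**Conclusion.** The inconsistency is real and should be fixed, but its reach is limited. Taken literally, 8.1 withholds the SAE label from serious events that neither the PI nor the sponsor thinks both unexpected and at least possibly related. The clearest losses face FDA: the annual SAE summary and the outcome follow-up reports. Monitoring after withdrawal may also be lost for expected but related events. For the IRB, IND sponsor and DSMB the loss is largely one of label.

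The conclusion assumes the more natural reading of Section 8 and rests on the conflict within the protocol, not on the content of the FDA definition. The documents give no rate of expected or unrelated serious events, so the number of participants affected cannot be stated. It would be too strong to say that the drug's anticipated harms will go uncounted: that needs Section 6 to be the expectedness reference, which the protocol does not say.

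**What to change.** Reconcile Sections 8 and 8.1. In 8.1, define an SAE by the listed outcomes only. Record expectedness and relatedness as separate attributes of each event, and let them trigger expedited reporting. At minimum, reword the 8.1 sentence so that it defines a *reportable* SAE for expedited reporting, and state that the Section 8 definition governs SAE counts, summaries and follow-up. In either case, say whether the Section 6 risk lists are the reference for judging an event expected and, if not, name the reference.

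The cost is protocol wording and a check that the adverse event form captures both attributes. The form is not in the documents, but Section 9.1 already calls for a causality determination. Compared with a literal use of 8.1, slightly more SAEs would be logged and summarised. No extra participant contact and no change to the statistical analysis are needed.

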10. If the study drug is well tolerated, the PI will be contacted and IDS orders for enough study drug/placebo will be ordered to sufficiently cover dosing for participants as described in drug distribution section.
11. Drug supply dispersal

- a. Participants will receive sufficient study drug/placebo supply. We will instruct participants to return all of the study drug packaging, including unused study drug and empty packaging at each study visit and/or at the time of discontinuation from treatment.
12. Study staff will review medication administration and use of the drug diary card with all participants. Participants will be asked to record the time they take the drug each day and any symptoms with severity rating and/or health events during the dosing period.
13. The study staff will review biopsy site care with participants and if indicated, remind participants to resume their normal anti-coagulation/anti-platelet/anti-diabetic medications.
14. Participants will be called 2 days after biopsy for assessment of biopsy healing. All participants will be given the option of returning for an Interim Visit for direct assessment if symptomatic.
15. Daily activity: Participants will be encouraged to begin or extend a daily walking routine with specific instructions and encouragement to progress in time and length as tolerated.

In order to track these changes over the course of the 12-week intervention, participants will be asked general questions about activity level, exertion level, and barriers to activity. Furthermore, the study nurse will ask about any progress as part of the interim study on-site and phone-based assessments.

The Daily Activity questions are not a study endpoint, but rather they are pragmatic tools to encourage motivation and behaviors of activity. Only the ActiGraph data are study endpoints.

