#### **2.4.3 Safety Analysis**

We will describe and descriptively compare proportions of those with clinical endpoints/adverse events such as hospitalizations, urgent clinic/ER visits, and death between the treatment groups, as using chi-square and Fisher's exact tests for dichotomous outcomes with such a small number of participants is unlikely to reliably demonstrate statistical significance.

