## 8.2 ADVERSE EVENTS REPORTING TIMELINES

Life-threatening or fatal unexpected adverse events associated with the use of the study drug or procedures must be reported to the DSMB Chair and to the IRB within 24 hours of discovery of the incident with subsequent follow-up submission of a detailed written report.

The FDA will be notified by telephone or facsimile transmission of a human adverse event that is fatal or life-threatening no later than 7 calendar days after receiving the respective human adverse event information, followed by the subsequent submission of a written IND Safety Report.

Serious and unexpected adverse events associated with the use of the study drug or procedures will be reported within 48 hours to the DSMB Chair and the IRB with subsequent follow-up submission of a detailed written report in accordance with the respective policies and procedures of the IRB. Written IND Safety Reports will be submitted to the FDA as soon as possible and, in no event, later than 15 calendar days following the investigator-sponsor's receipt of the respective adverse event information. All AE and SAE will be reported to the DSMB quarterly.

A summary report of the findings will be prepared and submitted to the regulatory agencies as required.

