## **9.2 DATA SAFETY MONITORING PLAN**

Monitoring of safety and data quality in the proposed study will be the responsibility of all personnel on the project, with primary responsibility and supervision by the Investigator. The Institutional Review Board will approve the Statement of Informed Consent for the study and provide institutional oversight of data and safety issues. The study protocol will be approved prior to recruiting or obtaining consent from any participants. Moreover, the study will be reviewed at a minimum of annual basis (or more frequently as deemed necessary) by the IRB committee. Each participant will sign the Informed Consent Form described above prior to participating in the study. To ensure participant safety, once participants are enrolled in the study, study staff will immediately report all adverse and serious adverse events to one of the Investigators. The Investigator will, per institutional requirements, report them to the IRB for their review. These events should also be communicated to the sponsor of the IND. With regards to the monitoring of data quality and protected health information, all required personnel proposed for this project will have the required human participants and confidentiality training, which includes information about maintaining data integrity and security. Confidentiality will be guarded using established procedures such as storing data in locked cabinets within locked offices or locked data rooms, coding by study identification numbers rather than any personally identifying information to avoid revealing the identity of participants, and aggregating data across participants. The key linking names and study identification numbers will be kept separately from the data sets with limited access by study personnel. Only study personnel will have access to the data sets on protected servers. In order to maintain the highest standard of data entry quality, all data will be double entered, with discrepancies highlighted so that they can be reviewed by the project coordinator. Oversight of all aspects of data management will occur with the Investigator.

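### The Section 8.1 entry rule for the adverse event form conflicts with all-event reporting elsewhere and, on its natural reading, leaves some events out of the Section 2.4.3 comparison of arms

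*Combined protocol and SAP*

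**What the plan says.** All references are to the combined protocol and SAP.

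- **Entry on the form (Section 8.1).** If "clinically important and unexpected adverse experiences or clinically important study-related adverse experiences occur, they will be recorded" on the adverse event case report form. No other section says what goes on that form.
- **Serious events (Section 8.1).** The trial's own definition narrows these to events that the principal investigator or the sponsor considers "to be unexpected and at least possibly related to the study and results in any of the following".
- **Definitions and grading (Section 8).** The FDA definitions of adverse and serious adverse events are adopted. Severity runs from Grade 1, which covers events with mild or no symptoms that need no intervention.
- **Reporting to the DSMB (Section 8.2).** "All AE and SAE will be reported to the DSMB quarterly".
- **Reporting to investigators (Section 9.2).** "study staff will immediately report all adverse and serious adverse events to one of the Investigators".
- **Collection from participants (Section 2.2.1).** Under Visit 4, item 12, the diary takes "any symptoms with severity rating and/or health events during the dosing period". The weekly telephone calls ask about symptoms, emergency room visits and hospitalizations, whatever their cause.
- **Analysis (Section 2.4.3).** The plan is to "descriptively compare proportions of those with clinical endpoints/adverse events such as hospitalizations, urgent clinic/ER visits, and death between the treatment groups". It is descriptive, with no formal testing, and no data source is named.

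**The concern.** Whether an event was unexpected, study-related or clinically important is a judgement about one case. The randomized comparison exists to show whether events are more frequent on nitrite, without relying on such judgements. If they decide which events are recorded, the comparison is made on a record that has already been sorted by presumed cause and importance.

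What is at stake is the tolerability profile. Section 6.1.1 lists in advance the effects anticipated with nitrite, among them hypotension, dizziness, headache and nausea. Section 10 expects that some participants will not tolerate treatment, and the synopsis presents the trial as a foundation for later studies. A by-arm account of milder symptoms is therefore a useful product of the trial. As written, two teams could both follow this protocol and produce different adverse event tables.

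**Working it through.** There is no plan figure to reproduce, because the documents state no expected adverse event rates by arm. The check is mainly a reading of the text, followed by an illustration on assumed rates.

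**Step 1: what the entry rule covers.** The rule has two limbs: (a) clinically important and unexpected, or (b) clinically important and study-related. Crossing the three judgements gives 2 × 2 × 2 = 8 combinations.

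| Clinically important | Unexpected | Study-related | Covered by the rule |
|---|---|---|---|
| Yes | Yes | Yes | Yes (a and b) |
| Yes | Yes | No | Yes (a) |
| Yes | No | Yes | Yes (b) |
| Yes | No | No | No |
| No | any (4 combinations) | any | No |

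Three combinations are covered and five are not. The events left out are those judged not clinically important and those judged both expected and unrelated. Expectedness alone does not exclude an important drug effect, because limb (b) still admits it. Lack of relatedness alone does not exclude an important event, because limb (a) still admits it.

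**Step 2: side by side with the other sections.** Most Grade 1 events in Section 8 would fail the test of clinical importance, so the lowest grade would be little used on the form. Sections 8.2 and 9.2 speak of all adverse events, and a form limited to three of the eight combinations cannot supply that list. The diary and the calls collect more widely, but no section says that their content is entered on the form or used in Section 2.4.3.

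**Step 3: link to the analysis.** The form is the only adverse event data record that the protocol names, so reading Section 2.4.3 as drawing on it is an inference, though a fair one. The events that Section 2.4.3 names are less exposed: the calls ask about emergency visits and hospitalizations directly, and most such events, like deaths, would probably be clinically important and unexpected.

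**Step 4: illustration on assumed rates.** Assume true risks of 20% on placebo and 40% on nitrite. With 35 per arm (Section 2.4.1) that is 0.20 × 35 = 7 and 0.40 × 35 = 14 participants. Assume at most one event per participant, so that recorded risk = true risk × share of events that pass the filter.

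| Share passing, placebo / nitrite | Recorded risks | Difference (points) | Ratio |
|---|---|---|---|
| 100% / 100% | 20% / 40% | 20 | 2.0 |
| 75% / 75% | 15% / 30% | 15 | 2.0 |
| 50% / 50% | 10% / 20% | 10 | 2.0 |
| 25% / 25% | 5% / 10% | 5 | 2.0 |
| 50% / 25% | 10% / 10% | 0 | 1.0 |
| 25% / 50% | 5% / 20% | 15 | 4.0 |

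Equal loss shrinks the absolute difference and leaves the ratio alone. Unequal loss can move the ratio either way. Removing only background events need not shrink the difference at all: if the 40% is 20% background plus a 20-point drug effect, dropping all the background leaves about 0% versus 20%, still 20 points.

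**Step 5: could the loss differ by arm?** Sections 2.3.5 and 2.3.10 leave some safety and care roles unblinded, and Section 10 provides for unblinding in certain events. Section 8.1 does not say who judges entry for non-serious events. Unequal loss therefore cannot be ruled out; nothing shows that it would occur.

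**The case against.** The strongest reply is that Section 8.1 states when an event will be recorded, not that other events are kept off the form. The word *only* does not appear, and the sentence stands in a section about reportable events. The Grade 1 category and the all-event wording of Sections 8.2 and 9.2 suggest that fuller recording was intended. Section 7.1 also lists participant diaries among source documents. All this is correct. It shows that the protocol can be read in two ways, not that the question is settled: Section 8.1 remains the only entry rule, and a conditional rule standing alone is naturally read as the limit.

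A reader might infer more than the documents support:

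- *That the DSMB will receive an incomplete list.* Section 8.2 promises it all adverse events. What can be said is that the form rule and that promise do not match.
- *That hospitalizations, emergency visits and deaths will be lost.* The calls and the unexpected limb should catch most of them.
- *That known nitrite effects are screened out because they are expected.* The study-related limb admits them when they are judged clinically important.
- *That the drug will look better tolerated by a calculable factor.* Proportional shrinkage needs equal loss in both arms and one event per participant, and it does not apply to the removal of background events. Section 6.1.1 classes several of the symptoms as rare, so the assumed 20% and 40% have no basis in the documents.

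It is also fair to say that Section 2.4.3 is descriptive, so no test, alpha level or power statement is touched.

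**Conclusion.** The point holds as an internal conflict with a consequence for the safety comparison. The entry rule in Section 8.1 does not agree with Sections 8, 8.2 and 9.2. On its natural reading, the comparison in Section 2.4.3 would miss events judged not clinically important and events judged both expected and unrelated.

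This rests on two readings: that the sole entry rule marks the limit of what is entered, and that Section 2.4.3 draws on the form. Both are reasonable and neither is stated. The size and direction of any distortion cannot be computed from the documents; the table shows only what different patterns of loss would do under assumed rates. The primary analysis is unaffected. The sections should be reconciled early, because events not entered as they occur may be hard to recover uniformly later.

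**What to change.** Reconcile Section 8.1 with Sections 8, 8.2 and 9.2 as follows.

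- Record every adverse event on the form, whatever its importance, expectedness or relatedness, from the first study procedure after consent to the final call one week after Visit 9. Starting only at first dosing would omit events from the baseline exercise tests and the pre-dose biopsy, whose risks Section 6.1.2 describes.
- Hold grade, relatedness and expectedness as separate fields, and use those judgements only to decide expedited reporting.
- State that adverse events found through the diary and weekly calls are entered on the form.
- Name the form as the data source for Section 2.4.3, and limit the comparison between arms to events after randomization. Events before randomization can be listed separately.

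The cost is protocol wording and more form entries. The diary and calls already gather the symptoms, and no visit or procedure is added.
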